8.2 Accrual

The estimated accrual period is 21 months, and total study duration (first patient enrolled to last patient off study) is 36 months.

8.3 Interim Analyses

Patients in Part A will be evaluated for dose-limiting toxicities during the first two cycles of treatment as outlined above in Section 7.1.

In Part B, an interim safety analysis will be performed after 6 patients are enrolled. If the DLT frequency exceeds 33%, study accrual will be halted and alternative dose and schedule of Lu-PSMA-617 may be evaluated based on the prior results of Part A of the study.

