Study Design	
This is a single-center Phase 1b open-label, study of PSMA-targeted radionuclide therapy with ^{177}Lu-PSMA-617 in combination with pembrolizumab in patients with mCRPC who have previously progressed on at least one prior androgen pathway inhibitor (e.g. abiraterone, enzalutamide, apalutamide). Patients must have at least three metastatic lesions which are PSMA-avid on baseline ^{68}Ga-PSMA-11 PET imaging.
 
In Part A of the study, patients will be enrolled sequentially into one of three treatment schedules with respect to timing of ^{177}Lu-PSMA-617 in relation to first dose of pembrolizumab (N = 6 patients per schedule):
 
Schedule 1) Priming dose of ^{177}Lu-PSMA-617 administered on Cycle 1 Day 1 followed by pembrolizumab 200 mg IV q 21 days starting Cycle 2 Day 1.
 
Schedule 2) Priming dose of ^{177}Lu-PSMA-617 administered concurrently with initiation of pembrolizumab on Cycle 1 Day 1.
 
Schedule 3) Priming dose of ^{177}Lu-PSMA-617 administered on Cycle 1 Day 1 following initiation of pembrolizumab on Cycle 1 Day -21.
 
The dose-limiting toxicity window will be Cycle 1 + Cycle 2 (i.e. 6 weeks following C1D1 administration of Lu-PSMA-617 across) in all three Schedule cohorts.
 
In Part A of the study, 6 patients will be enrolled to Schedule 1, then 6 patients to Schedule 2, and finally 6 patients will be enrolled to Schedule 3.
 
The starting dose of ^{177}Lu-PSMA-617 will be 7.4 +/- 15% GBq, which is the recommended phase 3 dose of the agent. If the DLT frequency attributable to Lu-PSMA exceeds 33% at any point after 6 evaluable patients have been enrolled in Part A, Dose Level -1 of ^{177}Lu-PSMA-617 will be investigated (4 Gbq +/- 15%) for the remainder of patients enrolled on study.
 
Using the data obtained in Part A, the recommended phase 2 dose and schedule of ^{177}Lu-PSMA-617 will be determined by the Principal Investigator using a combination of safety, efficacy, and immunologic effects of treatment from the first two cycles (and additional cycles of treatment when available).
 
In Part B of the study, an additional 25 patients will be enrolled at the recommended phase 2 dose and schedule to obtain additional safety, efficacy, and immunologic data pertaining to the treatment combination.

--------------	--

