3.1 Characteristics

This is a single-center Phase 1b open-label, study of PSMA-targeted radionuclide therapy with ¹⁷⁷Lu-PSMA-617 in combination with pembrolizumab in patients with mCRPC who have previously progressed on at least one prior androgen pathway inhibitor (e.g. abiraterone, enzalutamide, apalutamide). Patients must have at least three metastatic lesions which are PSMA-avid on baseline ⁶⁸Ga-PSMA-11 PET imaging.

In **Part A** of the study, patients will be enrolled in sequential fashion to one of treatment schedules with respect to timing of ¹⁷⁷Lu-PSMA-617 in relation to first dose of pembrolizumab (N = 6 evaluable patients per schedule):

Schedule 1) Priming dose of ¹⁷⁷Lu-PSMA-617 administered on Cycle 1 Day 1 followed by pembrolizumab 200 mg IV q 21 days starting Cycle 2 Day 1.

Schedule 2) Priming dose of ¹⁷⁷Lu-PSMA-617 administered concurrently with initiation of pembrolizumab on Cycle 1 Day 1.

Schedule 3) Priming dose of ¹⁷⁷Lu-PSMA-617 administered on Cycle 1 Day 1 following initiation of pembrolizumab on Cycle 1 Day -21.

The priming dose of ¹⁷⁷Lu-PSMA-617 will be 7.4 +/- 15% GBq, which is the recommended phase 3 dose of the agent. If the DLT frequency exceeds 33% including patients across the three schedules, Dose Level -1 of ¹⁷⁷Lu-PSMA-617 will be investigated (4 Gbq +/- 15%).

6 evaluable patients will be enrolled in each of the three cohorts in sequential fashion in Part A of the study. The DLT window will be Cycle 1 + Cycle 2. If the DLT frequency is \geq 33% for a

particular cohort, that dosing schedule will be determined to be non-tolerable and the next schedule will be evaluated. In addition, if the DLT frequency attributable specifically to Lu-PSMA-617 is $\geq 33\%$ after 6 or more evaluable patients are enrolled in Part A of the study, the dose of Lu-PSMA-617 will be reduced to Dose Level -1 (4 GBq +/- 15%) for the remainder of patients enrolled on study. If the DLT frequency attributable to Lu-PSMA-617 at Dose Level -1 is $\geq 33\%$ after 6 or more patients are treated at Dose Level -1, study accrual will be halted.

Using the data obtained in Part A, the recommended phase 2 dose and schedule of ^{177}Lu -PSMA-617 will be determined by the DSMC and Principal Investigator using a combination of safety, efficacy, and immunologic effects of treatment from the first two cycles (and additional cycles of treatment when available).

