In **Part B** of the study, an additional 25 patients will be enrolled at the recommended phase 2 dose and schedule to obtain additional safety, efficacy, and immunologic data pertaining to the treatment combination.

Number of Subjects

Approximately 43 patients will be enrolled over an accrual period of approximately 18 months (N ~ 18 patients in Part A; 25 patients in Part B).

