4.1.6 Dose Limiting Toxicities and Criteria for Dose De-Escalation

The starting dose level of ^{177}Lu -PSMA-617 is 7.4 GBq (+/- 15%).

Patients will be assessed for dose-limiting toxicities during Cycle 1 and 2 for patients enrolled in Part A of the study, defined as any of the following AEs occurring during Cycle 1 or 2:

- Any non-hematologic treatment-related AE \geq Grade 3, with the exceptions of Grade 3 nausea, vomiting, diarrhea, constipation, fever, fatigue, skin rash, or non-clinically significant laboratory abnormality that resolves to Grade \leq 2 within 72 hours with optimal medical management.
- Grade 4 thrombocytopenia, or Grade 3 thrombocytopenia with Grade > 1 bleeding or requirement for platelet transfusion.
- Grade 4 neutropenia lasting for > 5 consecutive days
- Grade ≥ 3 febrile neutropenia.

6 evaluable patients will be enrolled in each of the three cohorts in sequential fashion in Part A of the study. If the DLT frequency is $\geq 33\%$ for a particular cohort, that dosing schedule will be determined to be non-tolerable and the next schedule will be evaluated. In addition, if the DLT frequency attributable specifically to ^{177}Lu -PSMA-617 is $\geq 33\%$ after 6 or more evaluable patients are enrolled in Part A of the study, accrual will be temporarily halted and the dose of ^{177}Lu -PSMA-617 will be reduced to Dose Level -1 (4 GBq +/- 15%) for the remainder of patients enrolled on study. If the DLT frequency attributable to ^{177}Lu -PSMA-617 at Dose Level -1 is $\geq 33\%$ after 6 or more patients are treated at Dose Level -1, study accrual will be halted.

Patients who discontinue study for reasons other than treatment related toxicity during prior to the completion of two cycles of therapy, or those who discontinue study prior to receiving priming dose of ^{177}Lu -PSMA-617, will be considered inevaluable for purposes of DLT determination.

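### Part B has one numeric DLT look, at 6 of 25 patients, and the available text sets no later all-DLT limit for the other 19 at the starting dose

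*Combined protocol and SAP*

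**What the plan says.** Section 8.3 gives Part B one safety analysis: "In Part B, an interim safety analysis will be performed after 6 patients are enrolled". The consequence is: "If the DLT frequency exceeds 33%, study accrual will be halted and alternative dose and schedule of Lu-PSMA-617 may be evaluated". Section 3.1 sets the size of Part B: "In Part B of the study, an additional 25 patients will be enrolled at the recommended phase 2 dose and schedule". Section 8.4.2 then reports safety descriptively.

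Other rules elsewhere in the plan bear on toxicity:

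- **Part A cohort rule (Sections 3.1 and 4.1.6).** If DLTs reach 33% or more in a "particular cohort, that dosing schedule will be determined to be non-tolerable and the next schedule will be evaluated".
- **Lu-attributable dose-reduction rule.** The Abstract (Study Design) triggers it if the frequency "exceeds 33% at any point after 6 evaluable patients have been enrolled in Part A". Sections 3.1 and 4.1.6 give the same rule with a limit of 33% or more.
- **Dose Level -1 halt (Sections 3.1 and 4.1.6).** Accrual stops if the Lu-attributable DLT frequency "at Dose Level -1 is $\geq 33\%$ after 6 or more patients are treated at Dose Level -1, study accrual will be halted".
- **Appendix 2.** It provides continuous investigator review, monthly Site Committee review of grade 3-5 events, and DSMC review of serious suspected reactions at meetings every six weeks. The available text contains no numeric limit.

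On who is assessed, Section 4.1.6 says: "Patients will be assessed for dose-limiting toxicities during Cycle 1 and 2 for patients enrolled in Part A of the study".

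**The concern.** Six patients carry little information about a DLT rate, and Part B holds 25 of the 43 planned patients. Section 1.7.1 records that Part B was raised from 12 to 25. The look at six covers half of 12 but only 24% of 25. Once it is passed, the other 19 (76%) are treated with no stated count at which accrual stops for regimen toxicity.

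The other numeric rules do not fill this gap at the starting dose. One governs Part A cohorts, and the other two count only DLTs attributed to Lu-PSMA-617. Section 6.3.2.5 attributes colitis, pneumonitis and transaminitis to pembrolizumab, so those would not count. The one DLT reported in Section 1.7.1 is a Grade 3 inflammatory arthritis, described there among immune-related events.

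If a regimen with a 40% rate passed the look, 0.40 × 19 = 7.6 further DLTs would be expected.

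**Working it through.** **The plan's own figures.** The plan states no operating characteristic for the Part B safety look. Its only stated one is 93% power for response (10% against 40%, N = 25, two-sided 0.05; Section 8.1). The exact binomial reproduces it. Requiring 7 or more responses gives an upper tail of 0.0095 at 10% (6 or more gives 0.0334, above 0.025) and power of 0.926 at 40%.

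**Inputs for the safety look.** There is one look at n = 6 and a limit of 33% (Section 8.3), with N = 25. The true DLT rate p = 40% is an assumption, set just above the plan's own limit; the documents name no unacceptable rate.

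**What the limit means in counts.** 2/6 = 33.3%. If 33% is taken literally, 2/6 exceeds it and the halt is at 2. If 33% stands for one third, 2/6 does not exceed it and the halt is at 3.

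**Chance of passing the single look at p = 0.40**, from P(X = k) = C(6,k) × 0.4^k × 0.6^(6−k):

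- P(0) = 0.0467, P(1) = 0.1866, P(2) = 0.3110.
- Halt at 2/6: pass = 0.0467 + 0.1866 = 0.233.
- Halt at 3/6: pass = 0.233 + 0.311 = 0.544.

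**Including Part A.** A schedule is non-tolerable in Part A at 33% or more of its six patients, so 2/6 fails and at most 1/6 passes, with probability 0.233 at a 40% rate. The joint chance for one given schedule is 0.2333 × 0.2333 = 5.4%, or 0.2333 × 0.5443 = 12.7%. This ignores selection among the three schedules.

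**Adding cumulative looks at 12 and 18.** These figures come from an exact patient-by-patient recursion over 25 patients, with every DLT outcome known at each look. The boundaries are 2/6, 4/12, 6/18 or 3/6, 5/12, 7/18.

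| True DLT rate | Quantity | Halt at 2/6: one look → three looks | Halt at 3/6: one look → three looks |
|---|---|---|---|
| 40% | pass | 23.3% → 9.8% | 54.4% → 27.1% |
| 10% | halt | 11.4% → 12.2% | 1.6% → 1.8% |
| 20% | halt | 34.5% → 40.4% | 9.9% → 14.4% |
| 25% | halt | 46.6% → 56.2% | 16.9% → 26.8% |

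**Timing.** The look is triggered by enrolment, whereas the DLT window is six weeks from C1D1 (Abstract). Section 3.6.1 expects 2 to 3 patients per month. Six weeks is 6 × 12/52 = 1.38 months, so 2.8 to 4.1 more patients could enrol while the sixth patient's outcome matures. No accrual pause is stated for Part B.

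**The case against.** A reader might infer that the 19 later patients go unmonitored, or that Part B has no stopping rule after the sixth patient. The documents do not support either reading. Appendix 2 provides continuing review by the investigators, the Site Committee and the DSMC; what its available text lacks is a number. The Dose Level -1 halt is not confined to Part A, and the Abstract's open-ended wording of the Lu-attributable rule can be read to run into Part B. These narrow the gap, but they leave out DLTs attributed to pembrolizumab. Appendix 2 also has a heading, Increase in Adverse Event Rates, whose text was not in the copy reviewed, so a rule there cannot be excluded.

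A reader might also take 23% to 54% as the share of trials in which a 40% regimen slips through. It is not: it is conditional on that schedule being in Part B. With the Part A cohort included, the figure is 5.4% or 12.7%.

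The early data weigh against a 40% rate. Section 1.7.1 reports one DLT among 14 Part A patients. If all 14 were evaluable (not stated) and are pooled over schedules, the chance of at most one at 40% is 0.6^14 + 14 × 0.4 × 0.6^13 = 0.8%. That is some reassurance, but it is not specific to the schedule chosen.

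Finally, extra looks cost something. At a true 25%, below the plan's own limit, false halts rise by about 10 points. This stands and should be weighed openly.

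**Conclusion.** The point holds in a limited form. Section 8.3 gives Part B one numeric DLT look, at 6 of 25 patients. At the starting dose, no available text sets a later limit on all regimen DLTs for the other 19. At an assumed 40% rate, and given that the schedule has reached Part B, the look is passed with probability 23% or 54%. That spread comes entirely from whether 2/6 counts as exceeding 33%.

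The result rests on the assumed 40% rate, independent patients, fully known outcomes at the look, and no rule in the Appendix 2 text that was not available. It is a worthwhile, inexpensive strengthening of safety monitoring; it does not show that oversight is absent.

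**What to change.** 1. Check the Appendix 2 text on increased adverse event rates. If it already sets a numeric limit for Part B, cross-refer to it in Section 8.3.
2. Reconcile the two forms of the limit. The Abstract, Section 1.7.1 and Section 8.3 require more than 33%; Section 4.1.6 uses 33% or more; Section 3.1 uses both. State the result as counts. Which form applies is for the investigators to decide.
3. Keep the look at six, but base it on Part B patients who have completed Cycle 2 or had a DLT. Apply the same reconciled limit to the cumulative Part B count at 12 and 18 such patients: 2/6, 4/12, 6/18 or 3/6, 5/12, 7/18. State whether accrual continues while outcomes mature.
4. State in Section 4.1.6 that DLT assessment and evaluability apply in Part B. Correct the Section 8.3 pointer for DLTs, which leads to Section 7.1 on target lesions.
5. Report the operating characteristics in Section 8.3, including the false-halt rates at 10%, 20% and 25%.

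The cost is short edits to Sections 8.3 and 4.1.6, consistent wording in the Abstract and Sections 1.7.1 and 3.1, and two brief summaries for the DSMC, which already meets every six weeks. The statistical price is the rise in false halts shown in the table.

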1.7 Study Rationale

Despite encouraging data of ¹⁷⁷Lu-PSMA in men with advanced prostate cancer, the responses are limited in duration. Rather than attempt to continue men on treatment that may become ineffective or lead to excessive toxicity, we will utilize Lu-PSMA RLT in a novel way, via immunologic priming with subsequent pembrolizumab to maintain response in a durable fashion. In this Phase 1b dose escalation/expansion study we will garner the necessary safety and preliminary efficacy data to enable a decision whether to proceed to phase 2/3 study with this treatment combination.

1.7.1 Rationale for the Starting Dose and Proposed Dose Schedules of ¹⁷⁷Lu-PSMA-617 in Combination with Pembrolizumab

The proposed starting dose of ¹⁷⁷Lu-PSMA-617 will be 7.4 Gbq (+/- 10%), which is the recommended phase 2/3 dose of the compound as monotherapy. In the aforementioned prospective single arm phase 2 study of ¹⁷⁷Lu-PSMA-617 in 30 patients with mCRPC, the dose utilized was 8 Gbq (+/- 10%), which yielded acceptable safety and dosimetry results as outlined below:

Non haematological attributable to LuPSMA:

[figure not shown]
Toxicity	G1/2 (%)	G3/4 (%)
Dry mouth	63	0
Nausea*	50	0
Vomiting*	20	0
Fatigue	17	3
Dry eyes	7	0
Bone pain	7	3
Anorexia	7	0
Infusion related reactions	0	0
Renal toxicity	0	0

Haematotoxicity:

Toxicity	G1/2 (%) (baseline)	G1/2 (%) (any cause)	G3/4 (%) (LuPSMA)
Haemoglobin	80	73	23
Neutrophils**	0	40	10
Platelets	17	43	27
			13

* transient and self-limiting within first 24 hours

** no episodes of febrile neutropenia

[figure not shown]

For the current study, we will investigate a single planned priming dose of ^{177}Lu -PSMA-617 at a starting dose of 7.4 GBq (+/- 10%), in combination with the FDA-approved dose and schedule of pembrolizumab of 200 mg IV every 21 days. Given the non-overlapping toxicities between these two agents, the safety profile of repeated ^{177}Lu -PSMA-617 dosing demonstrated in the prior phase 2 study, and the fact that we are planning a single dose of ^{177}Lu -PSMA-617, this is an acceptable starting dose level.

If the DLT frequency exceeds 33% during Cycles 1 and 2 for the first 6 patients enrolled on Part A of the study, a lower dose level (Dose Level -1) of ^{177}Lu -PSMA-617 (4 GBq +/- 10%) will be investigated for subsequent patients enrolled in Part A.

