3.6 Study Timeline

3.6.1 Primary Completion

The study is anticipated to accrue 2-3 patients per month for an estimated accrual period of 21 months. The study is expected to reach completion for analysis of primary and secondary endpoints approximately 36 months from first patient enrolled.

4 Study Treatment

Treatment regimen

^{177}Lu -labeled PSMA is a PSMA-targeted radioligand that will be produced under Current Good Manufacturing Practice (CGMP) regulations.

In **Part A** of the study, patients will be enrolled in sequential fashion to one of three treatment schedules with respect to timing of ^{177}Lu -PSMA-617 in relation to first dose of pembrolizumab (6 evaluable patients per schedule):

Schedule 1) Priming dose of ^{177}Lu -PSMA-617 administered on Cycle 1 Day 1 followed by pembrolizumab on Cycle 2 Day 1.

Schedule 2) Priming dose of ^{177}Lu -PSMA-617 administered concurrently with initiation of pembrolizumab on Cycle 1 Day 1.

Schedule 3) Priming dose of ^{177}Lu -PSMA-617 administered on Cycle 1 Day 1 following initiation of pembrolizumab on Cycle 1 Day -21.

Pembrolizumab will be given at the FDA approved dose of 200 mg via IV every 3 weeks.

Dose-limiting toxicity data, additional safety data beyond Cycle 2 where available, along with efficacy and pharmacodynamic data, will be utilized to determine the recommended phase 2 dose and schedule of ^{177}Lu -PSMA-617 in combination with pembrolizumab to be utilized in Part B of the study.

4.1 ^{177}Lu -PSMA-617

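### The Part B safety stop in Section 8.3 is keyed to six patients enrolled; it requires neither completed 6-week DLT windows nor evaluable patients, and Section 4.1.6 assesses DLTs only in Part A

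*Combined protocol and SAP*

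**What the plan says.** Section 8.3 sets one numerical check for Part B: "an interim safety analysis will be performed after 6 patients are enrolled. If the DLT frequency exceeds 33%, study accrual will be halted". An alternative dose and schedule may then be considered.

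The DLT window is Cycles 1 and 2, which the Abstract (Study Design) gives as "6 weeks following C1D1 administration of Lu-PSMA-617". Section 4.1.6 assesses DLTs "during Cycle 1 and 2 for patients enrolled in Part A of the study". The Abstract (Safety Assessments) ties the definition to the dose-escalation period, and 8.3 itself names Part A when it describes DLT evaluation. For the definition, 8.3 points the reader back with the words "as outlined above in Section 7.1", but Section 7.1 is about measurable disease and target lesions.

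Section 4.1.6 also has an evaluability rule. Patients who leave before two cycles for reasons other than treatment-related toxicity, or before the priming dose, "will be considered inevaluable for purposes of DLT determination". Section 8.3 does not refer to it.

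On a related matter, the trigger for reducing Lu-PSMA to 4 GBq is stated five times. Two statements cover DLTs from either agent: Section 1.7.1, "If the DLT frequency exceeds 33% during Cycles 1 and 2 for the first 6 patients enrolled on Part A of the study", and the first statement in 3.1, "If the DLT frequency exceeds 33% including patients across the three schedules". Three count only DLTs attributed to Lu-PSMA: the Abstract (Study Design), the second statement in 3.1, and 4.1.6.

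**The concern.** A DLT frequency means what it should only when each patient in the denominator has been observed for the whole window. A patient enrolled last week adds one to the denominator and almost nothing to the numerator, so an early count understates the rate. Section 8.3 requires neither a completed window nor an evaluable patient, and no text extends DLT assessment to Part B, so the rule has no stated definition to work with.

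Part B holds 25 of the 43 patients, and this is the only numerical stop specific to Part B in the text available. If it is applied early, a regimen that is too toxic is less likely to be halted at the one point where the plan says it would be.

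**Working it through.** **The plan's own figures.** The plan gives no operating characteristics for this rule. Its one computed design figure, 93% power in Section 8.1, reproduces (exact binomial, 7 or more responses in 25: power 0.926 at 40%), but nothing below depends on it.

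**Inputs from the documents.** Look after 6 enrolled (8.3). Window of 42 days from C1D1 (Abstract). Accrual from Section 3.6.1: "The study is anticipated to accrue 2-3 patients per month".

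**Assumptions.** A month of 30.4 days, even spacing, first dose on enrolment, Schedule 1 or 2 carried forward, independent patients, and DLT onset uniform over the 42 days.

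**Threshold.** 2/6 = 33.3%, which exceeds 33% read to the digit, so two DLTs trigger the halt. If 33% stands for one third, three are needed.

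**Windows complete at the sixth enrolment.** Spacing is 30.4/2 = 15.2 days or 30.4/3 = 10.1 days. Days since C1D1 for the six patients are:
- 2 a month: 76, 61, 46, 30, 15, 0, so three have reached 42 days
- 3 a month: 51, 41, 30, 20, 10, 0, so one has

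Under Schedule 3 the first pembrolizumab dose is 21 days before C1D1, so 63 days must pass from the start of treatment, and one or none has completed.

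**Complete windows.** P(X ≥ 2) = 1 − (1−p)^6 − 6p(1−p)^5. At p = 0.2 this is 1 − 0.262 − 0.393 = 0.345.

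**Early look.** Patient i's DLT has been seen with probability p × min(1, t_i/42), where t_i is days since C1D1. P(at least 2 seen) is the exact sum over six independent patients with these unequal probabilities. For a later look, the lag is added to every t_i. Ranges run from 3 to 2 patients a month.

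| True DLT rate | At sixth enrolment | 14 days later | 30 days later | All windows complete |
|---|---|---|---|---|
| 20% | 0.138–0.189 | 0.240–0.265 | 0.318–0.321 | 0.345 |
| 30% | 0.271–0.357 | 0.435–0.472 | 0.544–0.549 | 0.580 |
| 40% | 0.418–0.531 | 0.618–0.659 | 0.732–0.737 | 0.767 |

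At a true rate of 10% the chance of stopping is 0.114 on complete windows and 0.039–0.056 at the sixth enrolment.

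**Sensitivity to onset, look at the sixth enrolment, rates of 20%, 30% and 40%.**
- All DLTs in Cycle 1: 22–24%, 40–44%, 59–63%
- All DLTs in Cycle 2: 7–14%, 14–28%, 23–43%

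The direction is the same in both cases; only the size changes.

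**Are these rates plausible?** Section 1.7.1 reports one DLT in 14 Part A patients. If all 14 were assessable, the exact 95% interval is 0.2% to 34%, so 20–30% is not excluded and 40% is a stress case.

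**Enrolment while waiting, without a pause.** 42/15.2 = 2.8 to 42/10.13 = 4.1 further patients, or 63/15.2 = 4.1 to 63/10.13 = 6.2 under Schedule 3.

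**Dose-reduction trigger.** Schedule 1 took the first six patients (Section 3.2), and the only DLT reported among the first 14 was on Schedule 2, so the Section 1.7.1 rule for the first six cannot have fired. For the pooled rule in 3.1, if all 14 were assessable, the most that Part A can reach is (1 + 4)/18 = 28%, below 33%.

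**The case against.** The strongest reply is that 8.3 gives an earliest time, not a date. A reader might infer that it orders a count on the day the sixth patient enrols. The documents do not say that. A DLT is defined over two cycles, so a sensible team would wait, and Section 8.1 moves from patients enrolled per cohort to evaluable patients in total as if they were the same. This stands: the defect is a missing requirement, and the sixth-enrolment column is the worst case. Its lower ends also use 3 patients a month, whereas 43 patients in the planned 21 months is 2.05 a month (2.4 with the 18 months in Section 3.1).

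A reader might also infer that Part B is unmonitored. It is not. Appendix 2 provides monthly site-committee review of grade 3–5 events and DSMC meetings every six weeks. The study calendars are organised by schedule rather than by part, and they collect adverse events and weekly blood counts through Cycles 1 and 2. The Dose Level -1 halt would apply if that dose were in use. The text of Appendix 2 under its heading on increases in adverse event rates was not available for this review, so no claim is made about what else it provides. General review still does not replace a pre-specified count with a defined denominator.

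On the threshold, exceeding 33% in 8.3 and reaching at least 33% in 3.1 and 4.1.6 lead to the same action at 2 of 6 unless 33% means one third.

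**Conclusion.** The point holds as a gap in the rule. Section 8.3 allows, but does not require, waiting for completed windows and evaluable patients, and nothing in the available text carries DLT assessment into Part B. In the worst case, a look at the sixth enrolment with uniform onset, the chance of halting at 2 of 6 falls from 34% to 14–19% at a true DLT rate of 20%, from 58% to 27–36% at 30%, and from 77% to 42–53% at 40%. With a 30-day lag the loss is about 2–4 points. The size rests on even accrual, dosing at enrolment and the onset pattern; the direction does not depend on the onset pattern. It is worth correcting but does not undermine the design.

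The dose-trigger conflict is real on the page, and Section 3.1 contradicts itself, but it is secondary. A reader might infer that it affected dosing in Part A; the reported data do not support that. Nor are the broader triggers any-cause rules, because non-hematologic DLTs must be treatment-related. A reader might also infer that a DLT attributed to the regimen as a whole must count against Lu-PSMA. Section 6.3.2.5 does not require this: for such events it applies both agents' dose-modification criteria, and it leaves final attribution to the principal investigator.

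**What to change.** 1. In 4.1.6, apply the DLT definition, the Cycle 1–2 window and the evaluability rule to Part B.
2. In 8.3, base the halt on the first 6 DLT-evaluable Part B patients with a completed window, or earlier once the threshold count is reached. Write the threshold as a count; 2 of 6 matches the Part A per-schedule rule of at least 33%. State whether accrual pauses while the sixth window completes.
3. Correct the reference in 8.3 from Section 7.1 to 4.1.6.
4. Align the dose-reduction wording in the Abstract, 1.7.1 and 3.1 to the Lu-attributed rule in 4.1.6.

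The cost is text edits and no extra patients or assessments. A pause costs up to 6 weeks (9 from first pembrolizumab under Schedule 3); without one, about 3–4 more patients (4–6 under Schedule 3) enter before the sixth is assessable. On complete windows, 2 of 6 halts a regimen with a true 10% DLT rate 11% of the time. Requiring 3 of 6 lowers that to 2%, but halting then falls from 34% to 10% at a 20% rate and from 77% to 46% at 40%. The choice of count is the sponsor's, and it should be written down.
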